6.3 Subject Exclusion Criteria

- Concurrent anticancer or radiation therapy. Patients must have completed all anticancer therapy > 4 weeks before the start of study therapy. The date of last palliative radiation must be > 2 weeks from the start of study therapy. Palliative radiation is permitted on protocol with MSK PI discretion on treatment modifications.
- Patients, who have had a major surgery or significant traumatic injury within 4 weeks of start of study drug, patients who have not recovered from the side effects of any major surgery (defined as requiring general anesthesia) .
- Patients receiving chronic, systemic treatment with corticosteroids or another immunosuppressive agent. Topical or inhaled corticosteroids are allowed.
- Concurrent oral contraceptive use or hormonal replacement therapy.
- Use of an aromatase inhibitor, GnRH agonist and/or tamoxifen within the past 30 days. Patients previously on fulvestrant or a q3 month GnRH agonist must have discontinued these medications for at least 3 months.
- Concurrent use of potent CYP3A4 and/or P-glycoprotein inhibitors or potent CYP3A4 inducers (please see Appendices 3 and 4). Where possible, otherwise eligible patients should be switched to alternative agents; otherwise, they will be excluded from the study.

Potent CYP3A4 inducers decrease serum everolimus levels and should not be given concomitantly. Dose modifications of everolimus are not indicated in the presence of moderate CYP3A4 inducers [108]. Please refer to Appendix 3 for a complete list of potent and moderate inducers of CYP3A4.

Potent CYP3A4 and/or P-glycoprotein inhibitors can increase serum levels of everolimus and should not be co-administered. Moderate inhibitors may mildly-moderately increase serum everolimus levels, though there is no definitive evidence supporting a dose reduction [108]. Please refer to Appendix 4 for a complete list of potent and moderate inhibitors of CYP3A4.

- Any investigational drug received within one month of study enrollment.
- Uncontrolled brain or leptomeningeal metastases, including patients who continue to require glucocorticoids for brain or leptomeningeal metastases
- Other active malignancies that may influence outcome.
- Any severe, uncontrolled medical conditions that, in the opinion of the investigator, may be exacerbated by study therapy or affect with study participation including infection, diabetes, cardiopulmonary disease, active bleeding diathesis, infections including HIV, and gastrointestinal disease that could impair study drug absorption.
- Any psychiatric illness/social situations that would limit compliance with study requirements.
- Pregnant or nursing women.
- Patients with a known hypersensitivity to everolimus, letrozole, leuprolide and/or related compounds or their excipients.
- Patients who received any form of transplant and who are on any form of immunosuppressive therapy. However transplanted patients who are off immunosuppressive therapy for at least 4 weeks are allowed on the study, provided that any of their immunosuppressive-related toxicities have recovered to at least a grade 1.
- Known HIV positive with a CD4 count < 500 cells/mm³.
- Immunization with a live vaccine < 1 week of initiating study therapy or during therapy.
- BSA < 1 m²

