6.1 CRITERIA FOR SUBJECT ELIGIBILITY

6.2 Subject Inclusion Criteria

- Patients \geq 12 years old.

MEMORIAL SLOAN-KETTERING CANCER CENTER
IRB PROTOCOL

IRB#: 11-211 A(6)

- Pathologically confirmed diagnosis of advanced and/or unresectable FLL-HCC. This will be performed by the participating centers on submitted specimens. If the submitted material is insufficient for analysis, a repeat biopsy is recommended.
- ECOG performance status 0-2 (see Appendix 1); Lansky performance score of $\geq 60\%$ for patients 12-16 years old (see Appendix 2)
- Adequate hematologic, renal and hepatic function defined as:
 - Hematologic: ANC $\geq 1.0 \times 10^9/L$, platelets $\geq 50 \times 10^9/L$.
 - Renal: creatinine $\leq 2 \times$ upper limit of normal, or creatinine Clearance of $\geq 60 \text{ cc/mL}/1.73 \text{ m}^2$ for patients > 16 years old. For patients ≤ 16 years of age, creatinine Clearance of $\geq 70 \text{ cc/mL}/1.73 \text{ m}^2$ or serum creatinine based on the following chart:

Creatinine clearance or radioisotope GFR $\geq 70 \text{ ml/min}/1.73 \text{ m}^2$ or serum creatinine based on age/gender as follows:

Age	Maximum Serum Creatinine (mg/dL)	
	Male	Female
10 to < 13 years	1.2	1.2
13 to < 16 years	1.5	1.4
≥ 16 years	1.7	1.4

The threshold creatinine values in this Table were derived from the Schwartz formula for estimating GFR (Schwartz et al. J. Peds, 106:522, 1985) utilizing child length and stature data published by the CDC.

- Hepatic: total bilirubin $\leq 2 \text{ mg/dL}$, alanine and aminotransferase levels $\leq 5 \times$ upper limit of normal for age.
- Fasting blood glucose $< 1.5 \times$ upper limit of normal . If fasting glucose $\geq 1.5 \times$ upper limit of normal, adequate glycemic control (fasting glucose $< 1.5 \times$ upper limit of normal) for three weeks is recommended before starting protocol therapy.
- At least 1 target lesion measurable by Response Evaluation Criteria in Solid Tumors (RECIST 1.1) guidelines.
 - Target lesion(s) must not lie within a previously resected, irradiated, ablated, or chemoembolized area. If a lesion does lie in such an area, there must be evidence of a $\geq 20\%$ increase in diameter and/or the appearance of a new lesion on subsequent imaging in order for such a lesion to be considered a target lesion.
- Prior systemic therapy is allowed. Prior surgery, locoregional ablative or embolic therapies are also permitted provided that the criteria for measurable disease as outlined above are met.

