12.2.1 Measurable disease

- Tumor lesions must be accurately measurable in at least one dimension (longest diameter in plane of measurement recorded) and have a longest diameter of ≥ 10 mm by CT (slice thickness ≤ 5 mm) or MRI.
- Pathologically enlarged, measurable lymph nodes are ≥ 15 mm in the short axis on CT (slice thickness ≤ 5 mm) or MRI. Only the short axis is to be measured at baseline and on follow-up scans.
- Lytic or mixed lytic-blastic bone lesions with a soft tissue component are considered measurable disease if the soft tissue component is measurable by CT or MRI and meets the size criteria for measurability.
 - Bone scan, PET and plain films are inadequate techniques to measure bone disease, but can be used to verify the presence or disappearance of bony lesions.
- Lesions representing cystic metastases are considered measurable if they meet the size criteria for measurability. Where possible, non-cystic lesions are preferred as target lesions.
- Lesions sitting in an area previously irradiated or treated with locoregional therapy are only considered measurable if there has been evidence of progression in those lesions.

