12.2 Response criteria

12.2.1 Evaluation of target lesions

- Complete response (CR): disappearance of all target lesions and regression of all pathological lymph nodes (target and non-target) to < 10 mm in short axis diameter.
- Partial response (PR): $\geq 30\%$ reduction from baseline in the sum of diameters all target lesions.
- Progressive disease (PD): $\geq 20\%$ increase in the sum of diameters of all target lesions from the smallest sum on study AND an absolute increase of at least 5 mm. Also includes the appearance of any new lesion(s).
- Stable disease (SD): Meeting neither criteria for PR or PD using the smallest sum on study as the reference.

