14.0 BIOSTATISTICS

Primary efficacy endpoints for Part 1 of protocol

- The primary efficacy endpoints for Part 1 of the study is progression-free survival at 6 months (PFS6).
- A progression event refers to the first evidence of radiographic disease progression, clinical progression as determined by study investigators, or death.
- Imaging performed in 6 months will be used to determine PFS6.
- PFS6 will be defined as the percentage of patients who are alive and have not experienced a progression event as defined above at 6 months from the date that study therapy was initiated. Patients that come off study before the 6 months scan will be considered events for the primary endpoint analysis.
- PFS6 will be assessed using a Simon's minimax two stage design, hypothesizing an improvement in PFS6 from 40% to 64% with the study regimen. Sixteen patients will be enrolled onto each of Arms A, B and C for a total of 48 patients in the first stage. Accrual will stop till the progression status at 6 months is obtained on all 16 patients in each arm. If 6 or less patients in one arm are progression free at 6 months the regimen in that arm will be terminated; otherwise, if 7 or more patients are alive and progression free at 6 months, enrollment will be extended in that arm to 28 patients (maximum total of 84 patients). At the end of stage 2, the respective regimens will be declared promising if 15 or more of the 28 patients in each arm are alive and progression free at 6 months. The design assumes a type I error (falsely accepting a non-promising therapy) and type II error (falsely rejecting a promising therapy) both set to 10%.

Figure 4: Simon's minimax 2 stage design (schematic applicable for each study arm)

- The probability of early termination due to drug inefficacy is 53%. In the event that 2 or more arms show promising activity, we will use the “pick the winner” format based on the randomized phase II clinical trials approach proposed by Simon et al. In this case, the regimen that has at least 15 patients progression free at 6 months and exceeds by at least 2 patients the number of progression free patients in the second best arm would be declared the winner. The probability of selecting the better regimen is 85%; the probability that no regimen is selected is 7%, while the probability of a tie is approximately 6% [149].

Secondary endpoints

- Secondary endpoints are:
 - Median PFS
 - Median overall survival (OS)

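### Palliative radiation is allowed on study, but no rule says how a lesion irradiated after baseline is read for response or PFS6

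*Combined protocol and SAP*

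**What the plan says.** **Radiation.** One bullet of section 6.3 opens by listing "Concurrent anticancer or radiation therapy" as an exclusion, gives washout periods, and ends: "Palliative radiation is permitted on protocol with MSK PI discretion on treatment modifications". The discretion concerns treatment. Neither the body site nor the endpoint is mentioned.

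**Choosing lesions.** Section 6.2 requires that "Target lesion(s) must not lie within a previously resected, irradiated, ablated, or chemoembolized area", unless growth or a new lesion has since been shown. Section 12.2.1 (Measurable disease) says that lesions in irradiated or locoregionally treated areas "are only considered measurable if there has been evidence of progression in those lesions".

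**Reading lesions on study.** Section 12.2.3 (Reporting of target lesions) builds the baseline sum from all measurable target lesions. Section 12.2.1 (Evaluation of target lesions) defines partial response as a 30% or greater "reduction from baseline in the sum of diameters all target lesions". Neither makes an exception for a lesion irradiated later.

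**Endpoint.** Section 14.0: "A progression event refers to the first evidence of radiographic disease progression, clinical progression as determined by study investigators, or death". It adds: "Patients that come off study before the 6 months scan will be considered events for the primary endpoint analysis". Section 13.0 does not list radiation as a reason to stop study therapy.

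**The concern.** The protocol accepts before entry that an irradiated lesion is a poor gauge of drug effect, yet has no matching rule once treatment starts. Take a patient whose target lesion is irradiated in month 3. The patient stays on study and the lesion stays in the sum. Any shrinkage from radiation can help reach the 30% threshold, and local control can hold the sum below the progression threshold at the 6-month scan.

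PFS6 drives the stage 1 stop (6 or fewer of 16) and the final claim (15 or more of 28) in each arm. Each arm is judged against a fixed 40%, so similar use of radiation in all three arms would not protect either decision. Objective response is a secondary endpoint with the same exposure.

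**Working it through.** **Step 1. Look for a rule.**

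| Place | Covers radiation before target selection | Covers radiation after baseline |
|---|---|---|
| 6.2 | Yes, bars the lesion unless growth is shown | No |
| 12.2.1 Measurable disease | Yes | Not expressly; it defines what is measurable |
| 12.2.3 and 12.2.1, sum and response | – | No exception; all targets stay in |
| 13.0 | – | Not a reason to stop |
| 14.0 | – | Not an event, not a non-evaluable status |

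The reading that irradiated lesions count follows from this silence together with the all-target-lesions rule. No single sentence states it.

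**Step 2. Reproduce the design.** Inputs from section 14.0: p0 = 0.40, p1 = 0.64, n1 = 16, n = 28, stop at 6 or fewer, promising at 15 or more, both error rates set to 10%, early termination 53%.

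With X1 ~ Bin(16, p) and X2 ~ Bin(12, p):

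- P(stop early) = P(X1 ≤ 6)
- P(promising) = Σ over x = 7 to 16 of P(X1 = x) × P(X2 ≥ 15 − x)

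Results:

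- p = 0.40: P(stop early) = 52.7%, P(promising) = 9.9%
- p = 0.64: P(promising) = 90.2%, so the type II error is 9.8%

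The plan's figures reproduce. An exhaustive search for the minimax design returns the same boundaries.

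**Step 3. Sensitivity to misattribution.** Let c be the share of would-be PFS6 failures that radiation turns into successes. The documents give no radiation rate, so c is an assumption. The observed rate is p = 0.40 + 0.60c. The expected number of failures converted among 28 patients is 28 × 0.60 × c.

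| c | p | Failures converted per 28 | P(stop early) | P(promising) |
|---|---|---|---|---|
| 0 | 0.400 | 0 | 52.7% | 9.9% |
| 2.5% | 0.415 | 0.42 | 47.8% | 13.1% |
| 5% | 0.430 | 0.84 | 42.9% | 16.8% |
| 10% | 0.460 | 1.68 | 33.6% | 26.1% |

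c is the share of failures fully converted. It is smaller than the share irradiated unless every irradiated would-be failure becomes a success.

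**Step 4. Cost of counting radiation as an event.** Let d be the share of true successes irradiated and so counted as failures. Then p = 0.64 × (1 − d).

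| d | p | Power |
|---|---|---|
| 0 | 0.640 | 90.2% |
| 5% | 0.608 | 82.6% |
| 10% | 0.576 | 72.4% |

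This loss is why the event-counting version belongs in a sensitivity analysis and not in the primary rule.

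**The case against.** The strongest reply is that existing provisions already catch most such cases.

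- **Clinical progression is an event.** A symptomatic patient who needs palliation can be called a failure. This stands as a limit. But the call is discretionary, investigators are unblinded (section 15.2), and no criterion links the need for radiation to progression.
- **Progression elsewhere still counts.** New lesions, unequivocal non-target progression, or enough growth in other targets still give PD. A reader might infer that irradiation hides progression in general. It does so only where the irradiated lesion would have driven the reading.
- **Central review.** Section 16.1.2 makes responses at all sites subject to the lead centre's review committee, which can obtain the radiology. The committee has no written rule on irradiated lesions.
- **The measurability rule.** Section 12.2.1 is not expressly confined to radiation before baseline, so one could extend it to on-study radiation. Even then it would not say how the sum, the response or PFS6 is to be read.

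Three stronger readings are tempting but not supported.

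- **That section 6.3 contradicts itself.** The exclusion can plausibly be read as an entry rule and the permission as an on-study rule. The wording needs clarifying, but a contradiction is not established.
- **That radiation can only raise the success count.** A delay of more than 4 weeks is a removal criterion in section 13.0, subject to a study-chair exception, and coming off study before the 6-month scan is an event. Radiation can therefore also produce failures.
- **That the choice of a winning arm is biased.** The permission is the same in all three arms, and nothing in the documents suggests unequal use.

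**Conclusion.** The gap is real. The protocol permits on-study radiation without limit of site and leaves the reading of a lesion irradiated after baseline undefined. As written, shrinkage or control from radiation can be credited to the regimen as a response or a PFS6 success.

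The size cannot be found from the documents. The rise from 9.9% to between 13.1% and 26.1% holds for a true rate of 40%, for assumed conversion of 2.5% to 10% of would-be failures, and for no offsetting failures caused by radiation. If on-study radiation is rare, the effect may be negligible. The range shows that about one patient per arm is enough to move the error rate well past the 10% limit. It does not show that this will happen. The finding concerns endpoint rules only and takes no position on whether radiation should be allowed.

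**What to change.** 1. **Sections 12 and 14, lesion rule.** State that a lesion irradiated on study cannot contribute to CR or PR from the date of radiation. State that growth of that lesion, new lesions and progression elsewhere still count as PD. State that a patient whose only target lesion is irradiated is not evaluable for later response.
2. **Data.** Record the date, site and reason for each on-study course of radiation, and report these by arm. Treatment records are already collected (section 16.1), but none of the forms listed in section 16.1.1.4 is named for radiation.
3. **Analysis.** Keep the primary PFS6 rule. Add a sensitivity PFS6 that counts radiation to a target, new or enlarging lesion before the 6-month scan as an event. Report whether any stage or final decision changes.
4. **Section 6.3.** Make clear that the exclusion and the on-protocol permission apply at different times, or otherwise reconcile the two sentences. The clinical rule is not at issue here.

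**Cost.** Some added text, a short data entry and one extra tabulation. The response rate may be slightly lower. The sensitivity PFS6 is conservative because it also fails some true successes: power would be about 83% if 5% of them were irradiated. It should be read beside the primary result and not in its place.

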7.0 RECRUITMENT PLAN

Subjects referred to any of the four participating centers: Memorial Sloan Kettering Cancer Center (MSKCC), the University of California San Francisco (UCSF), Johns Hopkins University (JHU) and the Dana-Farber Cancer Institute/Brigham and Women's Cancer Center and the Massachusetts General Hospital Cancer Center (DF/BWCC/MGHCC) who are deemed eligible by pre-screening will be invited to participate in the trial. Potential subjects will be identified from clinic consultation lists. A total of 84 patients are needed to meet the study endpoints. An accrual rate of 2 patients/month across all 4 study sites is anticipated, with the projected completion of enrollment within 42 months.

The trial will be announced on the NCI clinicaltrials.gov, the MSKCC, and the Fibromellar Cancer Foundation websites.

8.1 PRETREATMENT EVALUATION

8.2 Within 4 weeks of study treatment

- CT chest/abdomen/pelvis with contrast and triphasic liver.
 - Patients who are allergic to CT scan contrast despite premedication, or in whom a CT scan is clinically contraindicated, may undergo an MRI of the abdomen/pelvis and non-contrast CT chest instead.
- Baseline bone age radiographs in patients 12-15 years old interpreted using the Greulich-Pyle atlas [147].
- Baseline bone mineral density test for all patients \geq 16 years old
- Routine screening for hepatitis B (including surface antigen and core antibody).

8.3 Within 2 weeks of study treatment including first day of treatment

- Complete medical history and physical examination, including ECOG performance status (Lansky performance status for patients 12-16 years old), height/weight/body surface area.
- Complete blood count (CBC) and differential, comprehensive metabolic panel (Na, K, Cl, HCO₃, BUN, creatinine, AST, ALT, alkaline phosphatase, glucose), calcium, phosphorus, LDH, and ammonia
- Liver function tests (total bilirubin, albumin, INR/PTT)
- Fasting glucose and lipid profile including triglycerides and total cholesterol.
- Urinalysis.
- Electrocardiogram
- AFP
- Baseline plasma neurotensin, unsaturated vitamin B12 binding capacity, and des- γ -carboxyprothrombin
- Baseline serum estrone, estradiol, testosterone and follicle stimulating hormone (FSH) in all patients.
- Quantitative PCR for hepatitis C and hepatitis B as applicable. If hepatitis B surface antigen and/or hepatitis B core antibody are positive, results must be reported **before** Cycle 1 Day 1 of study treatment. Hepatitis C and hepatitis B quantitative PCR, as applicable, will be repeated every 3 months.
- Patients known to be infected with hepatitis C will be monitored as clinically indicated.
- Patients will be asked to give a blood sample and have their biopsy specimen available for future research studies.

- Negative pregnancy test (serum hCG) result in women of child bearing potential within 7 days before Cycle 1 Day 1 of study treatment. Negative pregnancy test (serum hCG) on Cycle 1 Day 1 is adequate.

9.0 TREATMENT/INTERVENTION PLAN

The study drug leuprolide will be distributed to the all four participating institutions by a third party, Biologics, Inc. The study drugs letrozole and everolimus will be distributed to the all four participating institutions by Novartis Pharmaceuticals.

9.1 Part 1, Arm A: everolimus

- Everolimus will be administered by the respective institutions' pharmacies at the following doses:
 - Patients with a BSA $< 1.5 \text{ m}^2$ will receive everolimus 5 mg PO QD.
 - Patients with a BSA $\geq 1.5 \text{ m}^2$ will receive everolimus 7.5 mg PO QD.
- Patients will be instructed to take everolimus at home, at the same time each day, consistently with food or without food, and swallowed whole with a glass of water.
- Patients unable to swallow whole tablets will be instructed NOT to crush or chew them. Instead, they should be completely dissolved in 30 cc of water by gently stirring immediately before swallowing. After swallowing, the glass should be rinsed with another 30 cc of water then swallowed again to make sure the entire dose was administered [131].
- If a dose is missed, they will be instructed to take it as soon as they remember up to 12 hours past the scheduled dose time. If it is almost time to take the next dose, they will be instructed to skip the missed dose and just take the scheduled dose. They will be instructed NOT to take 2 doses at the same time [131].
- If vomiting occurs after taking Everolimus, the subject should not take a replacement dose on that day. The subject should resume taking Everolimus at the next scheduled dose on the following day. If vomiting persists, the subject should be instructed to notify the investigator. If a subject vomits what appears to be an intact tablet(s), the subject should not take a replacement dose on that day because it is not possible to determine how much drug has actually been absorbed.
- Patients will be provided with a pill diary to record the date and time of day that everolimus is taken.
- Everolimus may be held for a maximum of 4 weeks for toxicity (see Section 9.5).
- Treatment will continue until disease progression, global clinical deterioration, unacceptable toxicity and/or consent withdrawal.

